## Exclusion Criteria:

- Females with PID, pregnancy, or currently breastfeeding
- Females of reproductive age not on a highly effective method of contraception (i.e., IUD, Nexplanon, progesterone only depot injection with last injection <3 months, or oral contraceptive pill and last menstrual period <28 days prior)
- Known QT prolongation, ventricular arrhythmias including torsades de pointes
- Receiving concurrent drugs known to prolong QT interval (e.g., Class IA or Class III antiarrhythmics, antipsychotics, erythromycin, pimozide, moxifloxacin, tricyclic antidepressants).
- Receiving strong or moderate CYP3A or P-gp inducers, strong CYP3A or P-gp inhibitors, moderate CYP3A or P-gp inhibitors or sensitive CYP3A4 substrates that prolong QT interval
- Moderate or severe liver impairment
- Renal failure requiring dialysis
- Known allergy to doxycycline, other tetracyclines, and/or lefamulin
- Known liver disease
- Not willing or unable to undergo a test to confirm MG infection at baseline and tests of cure 21-28 days and 42-47 days after completion of lefamulin
- Not fluent in English and/or not able to provide written informed consent
- Referring physician unwilling or unable to provide needed patient information
- At the study physician's discretion
- Rectal MG infection only

# **Recruitment**

STI care in the US is decentralized and there is no single clinic where MG treatment failures receive care. Instead, cases come to the attention of our team when individual providers and patients throughout the country contact us, and through clinical consultation requests submitted to the STD Clinical Consultation Network (CCN), National Network of STD Clinical Prevention Training Centers (https://www.stdccn.org/render/Public). The study physician, [name], is a consulting physician in the CCN and handles requests for consultation. In addition to leveraging the CCN to link providers with the study team, we will also post the protocol on clinicaltrials.gov.

The referring provider for patients with documented symptomatic MG treatment failure will be the official point of contact. Patients who contact team members directly will be provided contact information for the study team and asked to have their health care provider contact the team.

## Enrollment and consent

After the referring provider obtains verbal consent from their patient to contact the study team, the study physician will conduct an initial telephone or zoom consultation with the referring provider to discuss the patient's case and to determine initial eligibility. The study physician will complete the case report form (CRF) as a UW ITHS REDCap form, the referring provider will

indicate that verbal consent was obtained in a UW ITHS REDCap form, and sign and date the form. The CDC has developed an MG Treatment Failure Case Report Form (CRF) to document and track treatment failures that was approved by the OMB in March 2021. We propose to use this CRF to document cases of treatment failure, allowing us to link with the eventual CDC process for tracking MG treatment failures. The study physician will abstract information on concomitant medications, and other relevant medical history, to confirm eligibility and enter this information into a UW ITHS REDCap form. Where available, the study physician will also abstract Gram stain results and chemistry panel with liver function test results.

Upon receipt of the CRF, a research coordinator will arrange a zoom discussion between the study physician and the patient to explain the study procedures, answer questions, and obtain written informed consent, using the UW ITHS REDCap electronic signature process for consent. The UW-ITHS-supported version of REDCap meets the FDA's Part 11 electronic system requirements. The additional clinical information and the CRF will be completed by the study physician during the discussion with the patient to confirm eligibility and prior to prescribing lefamulin (and doxycycline for patients randomized to sequential therapy).

#### Dispensing lefamulin (and doxycycline, as warranted)

[name] will be the prescribing physician of record and partner with the UW Harborview Medical Center Investigational Drug Services (HMC IDS) to check for drug interactions and/or contraindications to lefamulin (and doxycycline for patients randomized to sequential therapy). Lefamulin and doxycycline will be stored in and dispensed from the UW HMC IDS Pharmacy, which will serve as the pharmacy of record. This is a locked, temperature-controlled facility adjacent to the PHSKC Sexual Health Clinic that manages and dispenses all medications for research studies conducted at the Harborview campus. HMC IDS will be responsible for tracking, documentation, and return/disposal of any unused drug provided by Nabriva.

Upon receipt of a prescription from [name], HMC IDS will prepare the medication packet(s). The research coordinator will ship the medication packet(s) to the patient. Mailing antibiotics across state lines is permissible with an IND exemption in place, which is the case here. Per our consultation with a clinical trials pharmacist, "when a clinical study is found to be IND exempt [21 CFR 312.2(b)], the FDA has granted that study the same permissions as a study with an IND (such as placing investigational drug into interstate commerce). ... with a documented IND exemption, ... the drug can be shipped across state lines when a subject has been enrolled in the study [21 CFR 312.40]." (full text of letter noting on file in the regulatory binder). The FDA has granted this study an IND exemption, cross-referencing Nabriva Therapeutics' existing IND. In addition to the lefamulin tablets, the medication package will include a drug information sheet for lefamulin; contact information for any patient questions about the antibiotic, side effects, or both; a letter, which provides an overview of the study; a specimen collection instruction sheet for each specimen; a return shipment instruction sheet; and materials for patients to collect and return two specimens (one specimen for culture and assessment of MICs; the other specimen to confirm MG infection at baseline). For patients randomized to sequential therapy, the medication package will also contain doxycycline tablets and a drug information sheet for doxycycline.

#### **Culture Specimens**

Each medication package will include one Copan flocked swab, one vial of Copan Universal Transport Medium [UTM]), and materials and instructions for returning culture specimens to the UW Global Health STI Laboratory. Male patients will be instructed to collect a self-obtained meatal swab and place it into the tube containing UTM before the first dose of lefamulin (or doxycycline if randomized to sequential therapy) is taken. Female patients will be instructed to take a self-obtained vaginal swab as described above. Both types of self-obtained swabs have demonstrated comparable sensitivity and specificity for diagnostic testing relative to clinician obtained swabs, and are acceptable to patients. Additional culture specimen collection materials and instructions will be included along with the Aptima test kits mailed out for tests of cure (see below).

Upon receipt in the Global Health STI Laboratory at the UW, culture specimens will be stored immediately at -70°C or colder. They will subsequently be shipped in batches to [name] laboratory at Statens Serum Institute. [name] laboratory is one of only a few worldwide with the demonstrated capacity to consistently cultivate *M. genitalium* and perform antimicrobial resistance testing. His laboratory will perform the culture and susceptibility testing for lefamulin, as well as for azithromycin and moxifloxacin, under a separate contract. Performing culture and MICs will enable us to assess whether there is any pre-existing resistance to lefamulin, whether any resistance to lefamulin is selected for during treatment, and whether the efficacy of lefamulin differs for azithromycin-resistant and moxifloxacin-resistant strains.

## Tests of cure

Tests of cure will be performed in the UW Global Health STI Laboratory (laboratory director [name]). The Hologic Aptima MG assay, which we propose to use for tests of cure, has higher sensitivity and specificity than most other assays. Thus, test-of-cure windows when using this assay are generally longer (21-28 days) than when other assays are used. Furthermore, instances of MG recrudescing after an initial negative test subsequent to treatment have been reported, suggesting that additional follow-up after an initial test of cure is warranted in studies of novel antimicrobials. Therefore, we will perform two tests of cure (one at 21-28 days and one at 42-47 days after completion of lefamulin).

The research coordinator will ship Aptima test kits to enrolled patients, one 21-48 days, and one 42-47 days after completion of Lefamulin. In addition to the Aptima collection kit and instructions and shipping materials to return the Aptima tubes to the UW Global Health STI Laboratory, that package will also include materials and instructions for culture specimen collection as described above. Culture specimens will be shipped at the same time as the test of cure specimens.

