# Study Design

We propose to provide compassionate access to lefamulin and estimate the efficacy of lefamulin in treating antibiotic resistant MG through a coordinating center at the University of Washington (UW). We will enroll a total of 40 symptomatic patients with MG infections who have experienced treatment failure after moxifloxacin and/or other second or third line antimicrobials

or in whom moxifloxacin is contraindicated. Patients will be followed for 42 or 56 days, depending on the regimen they receive.

There is an increasing global trend to pre-treat MG infections with doxycycline to reduce organism load. There have also been several initial reports of treatment failure after a 7-day regimen of lefamulin alone, but successes after a regimen in which patients were pre-treated with doxycycline in the companion study in Melbourne, Australia. Therefore, we propose to also determine if pre-treatment with doxycycline is necessary. To simultaneously assess the efficacy of lefamulin alone (600mg orally twice daily for 7 days), and a regimen incorporating pre-treatment with doxycycline 100mg orally twice daily for 7 days followed by lefamulin 600mg orally twice daily for 7 days), we will randomize the first 20 patients to either Regimen A (lefamulin alone) or Regimen B (pretreatment with doxycycline followed by lefamulin) in a 1:1 ratio.

An interim analysis will be performed after the first 20 patients are enrolled to assess the efficacy of each of these two regimens for futility. Based on the results of this interim analysis, we will make one of three possible decisions:

- If neither of the regimens meet criteria for futility, we will continue randomizing patients to one of the two regimens until we have reached our target sample size of 40 patients (20 randomized per arm).
- If one of the regimens meets criteria for futility but the other regimen does not, we will drop the regimen that met futility criteria and continue to administer the other regimen to the remaining 20 patients for a total of 30 randomized patients in the retained regimen.
- If both regimens meet criteria for futility, we will halt the study and reassess the possibility of using alternative dosing regimens.

Criteria for futility are outlined in the section on sample size on p. 6.

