# Inclusion Criteria:

- Physician referral
- Persistent symptomatic urogenital MG infection documented by any NAAT 14-90 days after completion of the prior antimicrobial regimen for MG
- Low risk of reinfection defined as no unprotected sex with an untreated sex partner since completion of the prior antimicrobial regimen
- Male or female sex at birth
- ≥18 years of age
- English-speaking
- Able to provide written informed consent
- Able to undergo a test to confirm MG infection at baseline and tests of cure 21-28 days and 42-47 days after completing lefamulin

- Referring physician willing and able to provide needed patient information
- Living in the US

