## Clinical, symptom, adherence, and side effects data

In addition to the CDC MG Treatment Failure CRF, the study physician will ask about other aspects of the patient medical history and enter this information into a separate UW ITHS REDCap form (concomitant medications, other relevant medical history, etc.). Where available, the study physician will also obtain Gram stain results and chemistry panel with liver function test results.

We will also program electronic surveys, using the UW ITHS REDCap platform, that will be completed by the patient on the start date of the first antibiotic course, upon completion of the antibiotic regimen (lefamulin alone or lefamulin and doxycycline), and at the 21-28-day and the 42-47-day test-of-cure timepoints. The REDCap surveys will collect information on dates of

antibiotic use, symptoms, antibiotic adherence, sexual behavior, and side effects. We will also program electronic reminders to remind the patient to complete the REDCap surveys and to mail in the test of cure and culture specimens.

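### Test-of-cure kits are scheduled to ship during, or after, the window in which they must be used, and the stated follow-up of 42 or 56 days fits no single starting point

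*Combined protocol and SAP*

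**What the plan says.** The Tests of cure section fixes the testing schedule: "we will perform two tests of cure (one at 21-28 days and one at 42-47 days after completion of lefamulin". The Inclusion Criteria require that patients can undergo "tests of cure 21-28 days and 42-47 days after completing lefamulin". The same two windows appear in the Exclusion Criteria, in the section on clinical, symptom, adherence and side effects data, and in Outcomes. The first window defines the primary outcome and the second defines sustained cure, a secondary outcome.

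The next paragraph of Tests of cure then gives the mailing schedule. The research coordinator will "ship Aptima test kits to enrolled patients, one 21-48 days, and one 42-47 days after completion of Lefamulin".

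Two other sections show what reaches the patient and when. The medication package, described under Dispensing lefamulin, holds materials to "collect and return two specimens (one specimen for culture and assessment of MICs; the other specimen to confirm MG infection at baseline"; both are baseline specimens. Culture Specimens treats the test-of-cure kits as a separate mailing: "Additional culture specimen collection materials and instructions will be included along with the Aptima test kits mailed out for tests of cure".

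The REDCap surveys are to collect dates of "antibiotic use, symptoms, antibiotic adherence, sexual behavior, and side effects", and electronic reminders will "remind the patient to complete the REDCap surveys and to mail in the test of cure and culture specimens".

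On total follow-up, Study Design says: "Patients will be followed for 42 or 56 days, depending on the regimen they receive". It does not say from what day this is counted.

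**The concern.** The first kit's shipping range does not match the window of the test it serves. A kit sent on day 29 or later cannot yield a test on days 21-28. A kit sent late in days 21-28 leaves little or no time to arrive and be used.

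The specimen at stake carries the only primary outcome. Patients are spread across the US and collect it themselves. Data analysis limits each denominator to patients with complete data for that outcome and gives no rule for a test taken outside its window. The listed survey content contains no specimen collection date. On the text given, a late test could be lost, or counted as if it were on time. The numbers are small: the futility rule turns on the first ten patients per arm, and final arms have 20 or 30.

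The follow-up sentence is a smaller matter. Its two figures appear to be counted from different days, so it does not tell the reader when follow-up ends in either arm.

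**Working it through.** **Inputs.** Test windows: days 21-28 and 42-47 after completing lefamulin (Tests of cure, Inclusion Criteria, Outcomes). Ship ranges as written: days 21-48 and 42-47 (Tests of cure). Regimen lengths: A 7 days, B 7 + 7 = 14 days (Study Design). Stated follow-up: 42 or 56 days (Study Design).

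**1. First kit, as written.** Permitted ship days: 48 − 21 + 1 = 28. Ship days after the primary window closes: 48 − 29 + 1 = 20. Share: 20/28 = 71%.

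**2. Range read as days 21-28.** For a kit sent on day s, the days left in its window are:
- first kit, 28 − s: 7 for s = 21, falling to 0 for s = 28;
- second kit, 47 − s: 5 for s = 42, falling to 0 for s = 47.

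The documents give no time from dispatch to collection, so I assume a delay of t days and show a range. A ship day is usable if s + t does not pass the end of the window. That leaves 8 − t of 8 days for the first kit and 6 − t of 6 for the second, with a floor of 0.

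| Assumed delay t (days) | First kit, usable ship days of 8 | Second kit, usable ship days of 6 |
|---|---|---|
| 0 | 8 | 6 |
| 1 | 7 | 5 |
| 3 | 5 | 3 |
| 5 | 3 | 1 |
| 6 | 2 | 0 |
| 8 | 0 | 0 |

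These count ship days, not patients. Turning them into a rate of late tests would need the actual distribution of ship days.

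**3. Is there an earlier kit?** The medication package contains baseline materials only, and Culture Specimens describes the test-of-cure kits as mailed out later. The reminders concern completing surveys and returning specimens; they cannot help a patient whose kit has not arrived.

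**4. Follow-up.** I tried to reproduce 42 and 56 as the time to the second test. Days of treatment counted from the origin are added to 42 and 47, taking lefamulin to follow doxycycline without a gap.

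| Origin | Regimen A | Regimen B | 42 fits A? | 56 fits B? |
|---|---|---|---|---|
| First dose | 7+42 to 7+47 = 49-54 | 14+42 to 14+47 = 56-61 | no | yes |
| Start of lefamulin | 49-54 | 49-54 | no | no |
| Completion of lefamulin | 42-47 | 42-47 | yes | no |

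No single origin gives both figures. From first dose, 42 days ends 49 − 42 = 7 days before A's second window opens, and 56 days reaches only the first day of B's. The stated difference between arms is 56 − 42 = 14 days; the schedule gives 7 from first dose or 0 from completion. Even A's earliest and B's latest second test, counted from first dose, differ by only 61 − 49 = 12 days.

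**5. Effect on the primary outcome.** From first dose the primary windows are 7+21 to 7+28 = days 28-35 (A) and 14+21 to 14+28 = days 35-42 (B). Both lie inside the stated follow-up, so the follow-up line bears only on the second test.

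**The case against.** The strongest reply is that the upper limit of 48 is a misprint. The sentence just before it, and every other mention, says 21-28, and a literal 21-48 would let the first kit go out alongside or even after the second. The 71% would then measure a typing error. This largely stands: the figure describes the text and should not be read as an expected loss.

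Once corrected, the two ranges equal the two test windows, so the sentence may only label each kit by its timepoint. That is possible. But the sentence instructs a named role to ship on those days, and nothing elsewhere says that kits go out ahead. A coordinator who followed it would mail inside the window.

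It is also true that no harm can be quantified, that a kit sent on day 21 still has 7 days, and that Sample size already allows for up to 30% loss to follow-up. That allowance covers some missing outcomes. It does not cure late kits, and it says nothing about a late test counted as on time.

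The contents of the kit instructions are not given, so a collection date may be recorded there. That stands: the field is missing from the listed survey content but is not shown to be absent everywhere. Early mailing also carries a risk of early collection.

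Lastly, the follow-up line is a summary sentence, and the operative sections still require the second test for everyone. That is why it ranks as the lesser point.

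**Conclusion.** The concern holds and the plan should be changed. The first kit's shipping range contradicts the primary test window. Correcting the probable slip does not settle it, because each kit would still be dispatched during the window in which it must be used, with 7 to 0 days left for the first and 5 to 0 for the second. This rests on reading the day ranges as dispatch dates, which is what the sentence says, though perhaps not what was meant. The text permits late primary specimens but does not force them. How many would occur depends on ship day and transit time, which the documents do not give.

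The follow-up figures of 42 and 56 days share no origin. That affects only the description of the second test, a secondary outcome, and leaves the primary outcome untouched.

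**What to change.** - In Tests of cure, correct the range of days 21-48 and separate dispatch dates from collection dates.
- Mail each kit so that it arrives before its window opens, with an instruction not to collect before day 21 (first kit) or day 42 (second kit) after completing lefamulin. Time the existing electronic reminders to those days.
- Record the specimen collection date with the returned kit or in the existing REDCap test-of-cure survey, unless the kit paperwork already captures it, and state that this date decides whether a test is in window.
- In Study Design, restate follow-up with its origin so that it covers the whole second window: to day 54 (Regimen A) and day 61 (Regimen B) from first dose, or to day 47 from completion of lefamulin in both.

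The cost is an earlier mailing date, at most one added date field, and wording changes in two sections. The drawback is that some kits may be mislaid or used early and need replacing. A recorded collection date would reveal early use, though it would not prevent it.

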## Clinical, symptom, adherence, and side effects data

In addition to the CDC MG Treatment Failure CRF, the study physician will ask about other aspects of the patient medical history and enter this information into a separate UW ITHS REDCap form (concomitant medications, other relevant medical history, etc.). Where available, the study physician will also obtain Gram stain results and chemistry panel with liver function test results.

We will also program electronic surveys, using the UW ITHS REDCap platform, that will be completed by the patient on the start date of the first antibiotic course, upon completion of the antibiotic regimen (lefamulin alone or lefamulin and doxycycline), and at the 21-28-day and the 42-47-day test-of-cure timepoints. The REDCap surveys will collect information on dates of

antibiotic use, symptoms, antibiotic adherence, sexual behavior, and side effects. We will also program electronic reminders to remind the patient to complete the REDCap surveys and to mail in the test of cure and culture specimens.

## **Outcomes**

We will assess one primary outcome and five secondary outcomes.

- Primary Outcome
  - Microbiologic cure defined as a negative Aptima MG test 21-28 days after completing lefamulin
- Secondary Outcomes
  - Microbiologic cure, as defined above, after lefamulin alone compared to microbiologic cure after sequential treatment with doxycycline followed by lefamulin
  - Clinical cure defined as absence of symptoms, absence of visible discharge, and absence of other clinical signs (<5PMNs/hpf on Gram stained smear where available) 21-28 days after completion of the lefamulin
  - Reported adherence to lefamulin (defined by self-reported number of tablets taken)
  - Reported adverse events (defined by self-reported adverse events)
  - Sustained microbiologic cure defined as a negative Aptima MG test 42-47 days after completing lefamulin

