# Study population:

Symptomatic patients with MG treatment failure will be eligible. Treatment failure will be defined as persistent symptoms and a positive NAAT test after (a) moxifloxacin and/or (b) other second or third line antimicrobials (e.g., minocycline, omadacycline, other), or (c) when moxifloxacin is contraindicated. Additional inclusion and exclusion criteria are:

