# Side effects

We will collect data on the following potential side effects of lefamulin and of doxycycline through our electronic REDCap surveys upon completion of the regimen and at 21-28 days and at 42-47 days after completion of the regimen.

- Gastrointestinal complaints: diarrhea, nausea, vomiting
- Other systemic complaints: photosensitivity, excess vaginal yeast with itching
- Other (open text field for patients to record other events)

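### Clinical cure is not tied to symptoms at the first dose, so a patient already symptom-free then counts as cured; a small upward bias in one secondary outcome

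*Combined protocol and SAP*

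**What the plan says.** The Outcomes section lists clinical cure as a secondary outcome: "Clinical cure defined as absence of symptoms, absence of visible discharge, and absence of other clinical signs". The signs include "<5PMNs/hpf on Gram stained smear where available", and the assessment falls 21-28 days after lefamulin is completed. The definition names no qualifying symptoms and does not mention the patient's state at the start.

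The Data analysis section plans simple proportions with 95% confidence intervals. The denominator for each outcome is the patients with complete data on it.

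On symptoms at entry, the Study population section says "Symptomatic patients with MG treatment failure will be eligible", and the Inclusion Criteria require "Persistent symptomatic urogenital MG infection documented by any NAAT 14-90 days after completion of the prior antimicrobial regimen for MG". Under Enrollment and consent, the study physician confirms eligibility with the patient before prescribing. The medication is then prepared and mailed (Dispensing section).

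The section on clinical, symptom, adherence and side effects data describes a survey "completed by the patient on the start date of the first antibiotic course", repeated at the end of treatment and at both test-of-cure timepoints. The surveys cover "antibiotic use, symptoms, antibiotic adherence, sexual behavior, and side effects".

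The Side effects section includes "Other systemic complaints: photosensitivity, excess vaginal yeast with itching" among the complaints to be collected, "upon completion of the regimen and at 21-28 days and at 42-47 days after completion of the regimen".

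**The concern.** Cure implies a change from ill to well, but the definition looks only at the end state. Being symptomatic is an entry condition. It is documented at the qualifying test and can be rechecked at the eligibility discussion, but prescribing, packing and mailing come after that. The plan sets no maximum interval to the first dose and does not require symptoms on that day. MG infection itself is re-tested at baseline; the symptom outcome has no matching step.

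A patient who became symptom-free in that interval and stayed so, without signs, enters both numerator and denominator as a cure, and the clinical cure rate is overstated. With about 20 patients per arm, a few such patients would show.

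A second, lesser gap is that the plan does not say which symptoms count. Vaginal itching is listed as a possible side effect and is collected at the same 21-28 day timepoint, and no rule says whether it affects the clinical-cure score.

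**Working it through.** **The plan's own figure.** No precision is stated for clinical cure. The nearest figure is Table 2 (Sample size section), which gives exact 95% intervals for a cure proportion. With x cures in n patients, the lower limit is the 2.5% quantile of Beta(x, n−x+1) and the upper limit is the 97.5% quantile of Beta(x+1, n−x). For 17/20 this gives 62.11 to 96.79, as printed. All six intervals in Table 2 reproduce.

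**Patients symptom-free at the first dose.**
- n = 20 per arm: Study Design section, if neither regimen is dropped, taking outcome data as complete.
- m = patients symptom-free on the start-date survey who are still clear at 21-28 days. The documents give no rate, so m is assumed.
- x = patients scored as clinical cures, also assumed.

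The reported rate is x/n. The rate among patients who had symptoms to lose is (x−m)/(n−m). The difference is m(n−x) / [n(n−m)].

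For m = 2 and x = 15: reported 15/20 = 75.0%; restricted 13/18 = 72.2%; difference 2×5/(20×18) = 10/360 = 2.8 points.

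Other assumed values:

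| m | x = 17 (85%): restricted | Difference | x = 12 (60%): restricted | Difference |
|---|---|---|---|---|
| 1 | 16/19 = 84.2% | 0.8 | 11/19 = 57.9% | 2.1 |
| 2 | 15/18 = 83.3% | 1.7 | 10/18 = 55.6% | 4.4 |
| 3 | 14/17 = 82.4% | 2.6 | 9/17 = 52.9% | 7.1 |
| 4 | 13/16 = 81.3% | 3.8 | 8/16 = 50.0% | 10.0 |

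The overstatement grows with m and with the number of failures. For scale, the exact interval for 15/20 is 50.9 to 91.3, so a shift of 2.8 points is small beside sampling error. It is, however, always upward for patients of this kind, and more patients would not remove it.

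**Itching recorded as a side effect.** Each patient in 20 is worth 1/20 = 5 points. Suppose 17/20 are clinical cures (85%, 62.1 to 96.8) and itching from yeast is read as a symptom in some of them:
- 1 patient: 16/20 = 80% (56.3 to 94.3)
- 2 patients: 15/20 = 75% (50.9 to 91.3)
- 3 patients: 14/20 = 70% (45.7 to 88.1)

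These counts are also assumed. They show what the coding choice could be worth, not that the loss would occur.

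**The case against.** The strongest reply is that patients who are symptom-free at the start should be rare. Only symptomatic patients are eligible, and the study physician confirms eligibility with the patient before prescribing. That leaves mainly the dispensing and mailing interval, in patients whose symptoms persisted after failed treatment. This stands, and it is why the effect is called modest. It does not close the gap, because the recheck comes before shipping and the day-of-start information goes unused.

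A strict end-state definition is also a legitimate choice. That stands too, and the unrestricted result should remain in the report.

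A reader might infer that any symptom whatever counts, so that a woman with yeast itching is certainly scored as a clinical failure. The documents do not say this. The definition sits among urogenital signs, in a trial of urogenital infection. The surveys list symptoms and side effects as separate content, and the yeast item is under side effects. The survey questions themselves are not in the documents. Separate collection does not settle the scoring, however, so the point is ambiguous rather than shown either way.

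A reader might also infer that the longer antibiotic course in Regimen B biases the clinical comparison of regimens. The Outcomes section names a comparison between regimens for microbiologic cure only; clinical cure is a simple proportion. In Regimen B the doxycycline comes first, so it ends at least 7 + 21 = 28 days before the assessment. No rate of yeast symptoms by regimen is given. No bias in a planned comparison is shown.

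**Conclusion.** The point holds as a small improvement to one secondary outcome. As written, the plan would count a patient without symptoms at the first dose as a clinical cure if that patient remained clear. The direction is upward. The size rests on assumed counts: 2.8 points for 2 such patients when 15 of 20 are scored as cured, and from 0.8 to 10 points across 1 to 4 patients at 85% and 60%. The lower end is the more plausible, because entry requires symptoms and eligibility is confirmed before prescribing. The calculation assumes that these patients are still clear at 21-28 days; one who developed symptoms would count as a failure and pull the other way.

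The handling of itching needs a clarifying sentence and is not a demonstrated error. The primary outcome and the futility rule use microbiologic cure and do not depend on any of this.

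**What to change.** 1. Keep all components of clinical cure: symptoms, visible discharge, other signs, and Gram stain where available.
2. Restrict the clinical-cure denominator to patients who report at least one urogenital symptom on the start-date survey. In both regimens that survey falls on the day study antibiotics begin, so treatment can hardly have influenced it.
3. Report the unrestricted proportion alongside, with the number of patients excluded. State that a patient without a start-date survey appears only in the unrestricted result.
4. As a clarification, state that symptoms means urogenital symptoms. Report the result with and without failures due solely to the yeast and itching item in the Side effects section. Showing both avoids having to rely on the patient's own view of what caused a new vaginal symptom.

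The change uses surveys already planned and needs no further visits, specimens or patients. The cost is that a few patients leave the denominator of one secondary outcome, which widens its interval slightly.
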